**STUDY DESIGN & OBJECTIVE**

This is a randomized, double-blind, placebo-controlled trial designed to evaluate the effect of adding methadone to traditional continuous sedation on the duration of mechanical ventilation. The investigators plan to enroll 46 patients.

The primary aim of this study is to compare the duration of mechanical ventilation in patients who receive methadone in addition to traditional continuous sedation (treatment group) and those who receive traditional continuous sedation plus placebo (control group). For each group, the total number of days on the ventilator will be calculated and compared.

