## **INCLUSION/EXCLUSION CRITERIA**

### **Inclusion Criteria:**

- Mechanically ventilated patients with opioid consumption greater than or equal to 1,200 mcg of fentanyl or equivalent consumption of another opioid per day during the first 48 hours of intubation.

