## **TREATMENT SCHEDULE**

Patients will be randomized in a 1:1 ratio to one of the following Arms:

- Methadone capsules by NG tube/feeding tubes 3 times daily, every 8 hours, for 7 days or until extubation whichever occurs first
- Placebo capsules by NG tube/feeding tubes 3 times daily, every 8 hours, for 7 days or until extubation whichever occurs first

**Methadone /Placebo dose calculation:** Dosing of the study medication will be based on the doses of opioids they have received prior to initiation of methadone. All opioids received in the previous 24 hours will be converted to morphine equivalents using a conversion table found “Demystifying Opioid Conversion Calculations” and this will be reduced 25% due to lack of complete cross tolerance. The resulting dose will be converted to a methadone dose utilizing a formula described by Ayonrinde et al. The total daily dose calculated will be divided in 3 scheduled doses and will NOT EXCEED 60 mg per day.

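### The primary outcome, raw days on the ventilator, counts a death that cuts ventilation short as a short, favourable duration

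*Protocol*

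**What the plan says.** The Protocol, under STUDY DESIGN & OBJECTIVE, gives the aim: "The primary aim of this study is to compare the duration of mechanical ventilation" between methadone and placebo, each added to the usual sedation. The next sentence fixes the quantity: "For each group, the total number of days on the ventilator will be calculated and compared". The same section gives the size, "The investigators plan to enroll 46 patients", and TREATMENT SCHEDULE gives the allocation, "Patients will be randomized in a 1:1 ratio to one of the following Arms", so there are 23 patients per arm.

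The population is intubated patients with heavy opioid use (Inclusion Criteria: "Mechanically ventilated patients with opioid consumption greater than or equal to 1,200 mcg of fentanyl or equivalent consumption of another opioid per day"). Extubation is mentioned only as a stop for study drug, in TREATMENT SCHEDULE: "for 7 days or until extubation whichever occurs first". No visible section mentions death, a follow-up horizon, ventilator-free days or a competing event.

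**The concern.** Fewer ventilator days is evidently meant to be the good result. Yet the count stops for two opposite reasons, liberation and death, and the stated quantity treats them alike.

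Three errors become possible:

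- An arm with more early deaths on the ventilator can appear to benefit.
- The same deaths can hide slower liberation.
- An arm whose dying patients stay ventilated longer than its survivors can have a real benefit hidden.

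Randomisation and blinding do not remove the problem, because it lies in the outcome itself. With 23 patients per arm, a chance imbalance of a few deaths is enough to move the comparison, even if methadone has no effect on mortality.

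**Working it through.** **Inputs from the Protocol.** 46 patients at 1:1, so 46/2 = 23 per arm; outcome is raw ventilator days. The Protocol states no mortality rate, extubation rate, standard deviation, test or significance level, so no figure of its own bears on this point.

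**Assumptions, none from the Protocol.** Exponential times; two-sided Wilcoxon test at 0.05; rates as listed below. Scenarios (a) to (c) have no true effect on liberation. Percentages of significant trials come from simulation, 40,000 trials for the raw-day results in (a). Repeat runs agreed to within about one percentage point.

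**(a) Deaths shorten ventilation.** With independent hazards, mean days = 1/(extubation hazard + death hazard), and the share dying ventilated = death hazard/(sum of hazards). Extubation is 0.12/day in both arms and control death is 0.03/day, so 0.03/0.15 = 20% of controls die ventilated and the control mean is 1/0.15 = 6.67 days.

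| Methadone death hazard | Mean days, methadone | False benefit (days) | Raw days significant for methadone |
|---|---|---|---|
| 1 × control | 1/0.150 = 6.67 | 0 | 2.6% |
| 1.5 × | 1/0.165 = 6.06 | 0.61 | 4.7% |
| 2 × | 1/0.180 = 5.56 | 1.11 | 7.5% |
| 3 × | 1/0.210 = 4.76 | 1.90 | 16.1% |

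Counting whole days gives 2.4%, 4.5%, 7.2% and 15.8%. In the same four cases, ventilator-free days falsely favour methadone in 2.5%, 1.3%, 0.7% and 0.3% of trials, and a cause-specific log-rank test in 2.8%, 2.8%, 2.8% and 3.1%.

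Varying the control mortality at a 2-fold hazard:

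- 10% dying (0.0133/day): 7.50 versus 6.82 days, a false benefit of 0.7 days, significant in about 5% of trials.
- 30% dying (0.0514/day): 5.83 versus 4.49 days, a false benefit of 1.3 days, significant in about 11%.

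**(b) Deaths prolong ventilation.** A fixed share p dies ventilated after a mean of m days; the others are extubated after a mean of 1/0.12 = 8.33 days. Mean raw days = p·m + (1 − p)·8.33. With p = 1/3 on methadone and 0.20 on control, the difference is (0.333 − 0.200)(m − 8.33).

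| m (days) | Methadone | Control | Difference | Significant against methadone |
|---|---|---|---|---|
| 4 | 6.89 | 7.47 | −0.58 | 1.3% |
| 8.33 | 8.33 | 8.33 | 0 | 2.6% |
| 12 | 9.56 | 9.07 | +0.49 | 3.2% |
| 16 | 10.89 | 9.87 | +1.02 | 4.3% |

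The sign therefore turns on whether patients who die are ventilated for less or more time than those extubated alive.

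**(c) Deaths only after final extubation.** The count is unchanged: difference 0, significant in 2.5% of trials.

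**(d) Masking, an existence example.** Methadone slows extubation from 0.12 to 0.09/day and raises death from 0.03 to 0.06/day. Mean raw days are 1/(0.12 + 0.03) = 1/(0.09 + 0.06) = 6.67 in both arms, although 40% (0.06/0.15) rather than 20% die ventilated. Mean 28-day ventilator-free days are 17.2 on control and 12.9 on methadone. Significant harm is shown by raw days in 2.6% of trials, ventilator-free days in 21%, a subdistribution (Gray-type) test in 28% and a cause-specific log-rank test in 12%.

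**The case against.** The strongest reply is one of scope. Much of this Protocol concerns drug supply and handling, its statement of the objective is two sentences long, and a statistical analysis plan that is not shown may say how deaths are treated. That a death counts as a completed duration is the natural reading, but it is inferred from silence. This limits the finding: one cannot say that the trial has no rule for deaths. It does not remove it, because the Protocol names the primary quantity itself, and that quantity has the defect.

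The second reply is that every rate is assumed and the inflation is modest. It takes a tripled death hazard to reach about 16%, scenario (b) gives only 3 to 4%, and (d) was chosen so that the hazards add to the same total. All of that is true, and no size or direction should be claimed for this trial.

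The third is that the alternatives have drawbacks. Ventilator-free days can favour an arm through survival alone: with 33.3% of controls and 20% of methadone patients dying and no difference in liberation, they favour methadone in about 11% of trials. Stating how deaths are handled and reporting them by arm would be a lighter repair and would answer much of the concern. It would still leave the primary comparison resting on a number that cannot distinguish liberation from death.

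**Conclusion.** The concern holds, limited to the outcome wording under STUDY DESIGN & OBJECTIVE. It should be fixed, with medium confidence, since an unseen analysis plan may already do so.

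The defect in the definition needs no assumption: a shorter total can mean faster liberation or earlier death. Its effect on the result depends on the excess of deaths in one arm and on their timing, and the Protocol gives neither. Under the assumed rates, doubling the death hazard with 10% to 30% of controls dying ventilated gives a false benefit of 0.7 to 1.3 days. If those who die are ventilated for a mean of 12 to 16 days, the bias is 0.5 to 1.0 days against the arm with more deaths. There is none if the mortality patterns are equal.

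**What to change.** Before unblinding, reword the primary outcome so that death on the ventilator cannot count as a short, successful duration.

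- **Preferred:** time from randomisation to extubation alive, with death as a competing event. State which extubation counts if a patient is reintubated, and name the test, since cause-specific and subdistribution comparisons answer different questions.
- **Alternative:** ventilator-free days to day 28 after randomisation, with death by day 28 scored 0.
- **With either:** report mortality by arm, and raw ventilator days split into extubated alive and died, as secondary results.

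The cost is Protocol wording, vital status to day 28 and a little more analysis. The preferred outcome targets liberation; ventilator-free days combine liberation with survival. Both must be read beside mortality, because fewer deaths in one arm can move either without faster liberation.

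Power may rise or fall and cannot be computed from the Protocol. As an assumed example, take an extubation hazard doubled to 0.24/day, 20% control deaths, 23 per arm and several death-timing models. Power is 33–39% for raw days, 25–41% for ventilator-free days, 26–55% for the cause-specific log-rank test and about 15–38% for the subdistribution test.

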## **SCREENING/ENROLLMENT**

PI/Study coordinator will provide IDS with the following information:

1. Patient Name/MRN
2. Signed Drug order in EPIC with pts blinded dose
3. Last signed page of the consent form.
4. Time/date of drug needed

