## **RANDOMIZATION**

- Based on the above information provided by the PI, IDS/Central pharmacist will assign the next sequential treatment arm to the patient by referring to the study randomization sheet in the study binder (will be kept in the central binder to ensure the same randomization is not assigned to two different patients)
- Write in date, patient name, MRN on the randomization schedule

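### Total ventilator days, as worded, include days before randomisation. They add noise, not bias, and counting from randomisation with lead-in adjustment avoids this at almost no cost.

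*Protocol*

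**What the plan says.** Under Study Design & Objective the protocol sets the aim: "The primary aim of this study is to compare the duration of mechanical ventilation in patients who receive methadone", in addition to usual sedation, with those given placebo. It then states the measure, by group: "the total number of days on the ventilator will be calculated and compared". The planned size is given in the same section: "The investigators plan to enroll 46 patients". At the 1:1 ratio in Treatment Schedule that is 23 per arm.

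The inclusion criterion takes patients who are already ventilated and judges them on fentanyl above a threshold or "equivalent consumption of another opioid per day during the first 48 hours of intubation".

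The start of study drug is not tied to a set time after intubation. Treatment Schedule bases the dose on a window that moves with the start: "All opioids received in the previous 24 hours will be converted to morphine equivalents". Screening/Enrollment has the team tell the pharmacy, patient by patient, the "Time/date of drug needed". No section gives a latest time for enrolment.

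**The concern.** A total count of ventilator days has two parts: those before randomisation (the lead-in) and those after it. Only the second can respond to methadone. The inclusion criterion makes some lead-in unavoidable.

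A lead-in of the same length for everyone does no harm, since it cancels in the comparison. A lead-in that varies between patients adds variation that has nothing to do with treatment. Because enrolment time is left open, that variation is possible, and 23 per arm leaves little precision to spare. What is at stake is power. The validity of the comparison is not in question.

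**Working it through.** **Inputs from the protocol.** N = 46, 1:1, so 23 per arm; ventilation before entry; no cap on enrolment time. The protocol states no alpha, power, effect, standard deviation or test, so 46 cannot be reproduced. Everything below that needs such a figure is an assumption.

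**Step 1: algebra on the mean difference.** Let r = SD(lead-in)/SD(days after randomisation), and rho their correlation. Then

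SD(total)/SD(after) = √(1 + r² + 2·rho·r)

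Take two-sided 5% and the difference that 23 per arm detects with 80% power counting from randomisation: (1.960 + 0.842) × √(2/23) = 0.826 SD. For the same difference in days, power on total days is Φ(2.802/inflation − 1.960).

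- r = 0.5, rho = 0: inflation √1.25 = 1.118; 2.802/1.118 − 1.960 = 0.546; power 70.7%.
- r = 0.25, rho = 0: inflation 1.031; power 77.6%.
- r = 0.1, rho = 0: inflation 1.005; power 79.6%.
- r = 0.5, rho = +0.3: inflation √1.55 = 1.245; power 61.4%.
- r = 0.5, rho = −0.25: inflation √1.00 = 1; power 80.0%, no loss.
- r = 0.25, rho = −0.25: inflation 0.968; power 82.5%, a gain.

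The loss disappears once rho is at or below −r/2. The document gives neither r nor rho.

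**Step 2: simulation with skewed durations.** Days after randomisation = exp(ln 6 + 0.75z), multiplied by 0.55 in the treated arm. The lead-in is uniform over days 2-3, 2-5 or 2-7, with correlation rho induced by a Gaussian copula. There are 23 per arm, no deaths, two-sided 5%, and 20,000 trials per cell (standard error about 0.3 points). Unadjusted analyses use Mann-Whitney. Adjusted analyses t-test the residuals of the outcome ranks regressed on the lead-in ranks. Power in %, for enrolment over days 2-3 / 2-5 / 2-7:

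| Outcome | rho = 0 | rho = +0.3 | rho = −0.3 |
|---|---|---|---|
| Total days, unadjusted | 72.0 / 67.7 / 62.2 | 69.3 / 62.0 / 54.1 | 74.4 / 75.0 / 71.8 |
| Total days, adjusted | 72.2 / 70.9 / 70.1 | 75.5 / 74.8 / 73.7 | 75.4 / 74.5 / 73.2 |
| Days after randomisation, adjusted | 72.4 / 72.0 / 72.3 | 75.9 / 76.2 / 76.5 | 75.3 / 75.3 / 75.1 |

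Unadjusted days after randomisation give 71.9-73.1% in all nine cells. A constant 2-day lead-in gives 72.6%, so it costs nothing. Counting in whole days changes little (total days, rho = 0: 71.9 / 68.1 / 61.7%).

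The adjusted count from randomisation is at least as powerful as unadjusted total days in every cell. The margin runs from 75.3 − 75.0 = 0.3 points, which is within simulation error, to 76.5 − 54.1 = 22.4 points.

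**Step 3: validity.** Null rejection was 4.4-5.4% over all cells and methods. A separate simulation (sigma 0.7, lead-in of 2 days plus an exponential delay averaging 3 days) gave mean differences of −3.45 days from randomisation and −3.44 from intubation. The estimand in days is therefore the same. Its standard error rose from 1.44 to 1.70 days, and t-test power fell from 72% to 54%. With a mean delay of 1 day it fell only from 72% to 70%.

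**The case against.** The strongest objection is scope. Where the clock starts, and how re-intubation counts, are often left to a statistical analysis plan, and one may exist that settles both. The sentence in question is a brief statement of aim, and its word for the total could mean the sum over repeated intubations and not a count from intubation. This stands in part. The absence of a stated origin would not by itself be a point to raise. What remains is that the measure as worded takes in days that treatment cannot affect, and that a better version costs almost nothing. The fix keeps the sum over re-intubations.

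The second objection is size, and it stands. Every input to the power figures is assumed. The protocol gives no basis for enrolment spread to day 5 or day 7. Even a 2-day minimum is an assumption, because the criterion does not say that the whole 48-hour window must pass before entry. With enrolment over days 2-3 and independence, the loss is under 1 point.

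The third objection concerns the remedy, and it is right. Merely moving the origin to randomisation does not always help: at rho = −0.3, unadjusted total days have higher power (74.4% and 75.0% for the two narrower spreads) than unadjusted days after randomisation (71.9-73.1%). The adjustment therefore has to be part of the fix.

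A reader might also infer that counting earlier days biases the result or invalidates the test. It does neither: those days precede randomisation and are balanced in expectation.

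**Conclusion.** The point holds as a matter of precision, at low severity. As worded, the primary measure includes time before randomisation, and the protocol lets that time vary between patients. The difference in days is unbiased and type I error is unaffected. A ratio or percentage computed on total days would lie nearer to no effect, but the protocol specifies no such measure.

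Under the assumptions in the working, adjusted days after randomisation give about 72-77% power and unadjusted total days about 54-75%. Those ranges show what is possible. A reader might take the lower end as the trial's actual loss, but the document does not support that: it gives neither the spread of enrolment times nor their relation to later ventilation. The true effect may be negligible, and with a negative correlation it may run the other way.

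**What to change.** Define the primary outcome as all ventilator days accrued after randomisation, including days after any re-intubation. Adjust the comparison for time from intubation to randomisation as a baseline covariate. Keep total days from intubation as a descriptive secondary outcome. If total days must stay primary, adjust them for ventilator days before randomisation; in the working this recovers most of the loss at rho = 0 (70.1% against 62.2% for the widest spread).

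The cost is a few sentences, with no added patients or procedures. The Randomization section already requires staff to "Write in date, patient name, MRN on the randomization schedule", and the pharmacy already receives the time the drug is needed. Intubation time is not listed as a recorded item but must be known to apply the 48-hour criterion; it should be written down, with the clock time of randomisation if hours are to be used. The one drawback is that the primary figure compares less directly with published totals, which the secondary outcome covers.

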**BACKGROUND**

Short acting opioids such as morphine, hydromorphone and fentanyl are used, typically in combination with a benzodiazepine or propofol for pain management and sedation in ICU. Due to the nature of the pain experienced by this patient population, specifically those requiring mechanical ventilation, fentanyl's short duration of action frequently leads to the need for continuous infusion or frequent bolus dosing. Tolerance and physical dependence develop quickly. Methadone offers unique pharmacokinetic and pharmacodynamic profiles that may provide advantages over these opioids.

## **INCLUSION/EXCLUSION CRITERIA**

### **Inclusion Criteria:**

- Mechanically ventilated patients with opioid consumption greater than or equal to 1,200 mcg of fentanyl or equivalent consumption of another opioid per day during the first 48 hours of intubation.

### **Exclusion Criteria:**

- Allergy to methadone
- Admitted for head injury
- Admitted for seizure
- Seizure during admission, prior to enrollment
- Subjects at high risk for developing a prolonged corrected QT (QTc) interval
- Gastric residual volume  $\geq 200$  mL
- Suspected obstruction or ileus
- Nausea and vomiting
- Recent abdominal surgery
- Active upper or lower gastrointestinal bleeding
- Active order for no medications by mouth or Total parenteral nutrition (TPN)
- Pregnancy
- Subjects receiving neuromuscular blocker infusions
- Subjects taking antipsychotics at baseline

## **ADVERSE EFFECTS**

- Refer to the package insert, micromedex etc. for details

## **TREATMENT SCHEDULE**

Patients will be randomized in a 1:1 ratio to one of the following Arms:

- Methadone capsules by NG tube/feeding tubes 3 times daily, every 8 hours, for 7 days or until extubation whichever occurs first
- Placebo capsules by NG tube/feeding tubes 3 times daily, every 8 hours, for 7 days or until extubation whichever occurs first

**Methadone /Placebo dose calculation:** Dosing of the study medication will be based on the doses of opioids they have received prior to initiation of methadone. All opioids received in the previous 24 hours will be converted to morphine equivalents using a conversion table found “Demystifying Opioid Conversion Calculations” and this will be reduced 25% due to lack of complete cross tolerance. The resulting dose will be converted to a methadone dose utilizing a formula described by Ayonrinde et al. The total daily dose calculated will be divided in 3 scheduled doses and will NOT EXCEED 60 mg per day.

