## **DRUG PREPARATION AND DISPENSING**

**CAUTION: Controlled Substance- schedule II drug, follow appropriate laws and regulations**

1. Verify the signed drug order in EPIC and print the label.
2. The order will indicate the patient blinded dose in increments of 5mg
3. Locate the study drug supply per patient randomization, i.e; active or placebo
4. Unit dose each dose per patient randomization, e.g: If patient randomized to the active Methadone arm, at a daily dose of 60mg (divided into 3 doses= 20mg Q8h, so four capsules of 5mg strength will be in each unit dose foil)
5. Label each unit dose aluminum package with EPIC label and package and label enough doses for a 7 day treatment. Also label with "Note Dosage Strength"

stickers. One dose =X # of capsules. Place another EPIC label on the Ziplock bag containing all 21 doses= 7 day supply

6. Label with “Investigational Use Only Label”, “Save and Return All Unused Drug”
7. Deliver the bag to a member of the investigation team and the team will load it into the pyxis machine on the patient floor along with a drug data sheet.
8. The floor nurse will remove one dose at a time from the pyxis machine and administer.
9. If patient discontinues prior to the completion of the 7 day treatment. The remaining doses will be destroyed by [name] and team and destruction and quantity will be documented on the patient specific log with double signatures meeting control substance destruction requirements.
10. Reconcile each patient medication bag with the number of unit doses prepared, dispensed and then wasted or destroyed. The total should add up at the end.

DO NOT TUBE ANY STUDY MEDICATIONS

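### Do the conversion-based dose rule and the 5 mg capsule supply conflict with an add-on regimen given in three daily doses?

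*Protocol*

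**What the plan says.** STUDY DESIGN & OBJECTIVE states that the trial will "evaluate the effect of adding methadone to traditional continuous sedation on the duration of mechanical ventilation". The control group receives the same kind of sedation with placebo. BACKGROUND describes usual practice: "Short acting opioids such as morphine, hydromorphone and fentanyl are used, typically in combination with a benzodiazepine or propofol". Entry requires "opioid consumption greater than or equal to 1,200 mcg of fentanyl or equivalent consumption of another opioid per day".

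TREATMENT SCHEDULE gives one dose calculation for methadone and placebo alike. "All opioids received in the previous 24 hours will be converted to morphine equivalents"; then "this will be reduced 25% due to lack of complete cross tolerance"; a published formula, not reproduced in the protocol, turns the remainder into methadone. It continues: "The total daily dose calculated will be divided in 3 scheduled doses and will NOT EXCEED 60 mg per day".

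STUDY DRUG provides capsules of 5 mg only. DRUG PREPARATION AND DISPENSING says "The order will indicate the patient blinded dose in increments of 5mg" and works one example, 60 mg a day. No section says what happens to the running opioid once study drug starts, in which direction a calculated dose is rounded, or whether the three doses must be equal.

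**The concern.** Two things seem not to fit.

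- **Role of the drug.** Converting the whole opioid intake and then deducting for incomplete cross tolerance is how one opioid is exchanged for another. The objective describes an addition, and the sedation it is added to usually contains the very opioid being converted. If bedside staff, who do not know the arm, read the rule as a replacement, they might cut the infusion in placebo patients too. If they read it as an addition, the methadone arm carries extra opioid. Those would be different treatment contrasts, and either could affect ventilator days, the primary outcome.
- **Capsules.** A calculated daily dose divided by three will often not be a whole number of 5 mg capsules. The dose given would then differ from the dose calculated, by an amount that depends on an unstated rounding convention.

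**Working it through.** **The protocol's own example** (DRUG PREPARATION AND DISPENSING): 60 / 3 = 20 mg per dose; 20 / 5 = 4 capsules; 3 × 7 = 21 doses for the week. All three figures reproduce.

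**Equal doses.** The daily dose is 3 × k × 5 mg with k = 1 to 4, that is 15, 30, 45 or 60 mg. Of the 12 multiples of 5 mg up to 60, eight (5, 10, 20, 25, 35, 40, 50, 55) do not split equally.

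| Calculated daily dose | Per dose | Rounded down | Rounded up |
|---|---|---|---|
| 20 mg | 6.67 mg | 15 mg (−25%) | 30 mg (+50%) |
| 40 mg | 13.33 mg | 30 mg (−25%) | 45 mg (+12.5%) |
| 50 mg | 16.67 mg | 45 mg (−10%) | 60 mg (+20%) |

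Rounding each dose to the nearest 5 mg errs by at most 2.5 mg per dose, so 3 × 2.5 = 7.5 mg a day.

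**Unequal doses.** Neither TREATMENT SCHEDULE nor ADMINISTRATION says the three doses are equal. Then 20 = 10 + 5 + 5, 40 = 15 + 15 + 10 and 50 = 20 + 15 + 15 are exact, as are 25, 35 and 55. Only 5 and 10 mg a day would leave a scheduled dose empty.

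**How often rounding arises.** The conversion figures are external, so this rests on assumption. At the entry minimum of 1,200 mcg fentanyl a day, suppose 10 to 30 mg morphine equivalent per 100 mcg and a morphine-to-methadone ratio of 3:1 to 20:1.

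- Morphine equivalent: 12 × 10 = 120 mg to 12 × 30 = 360 mg.
- After the reduction: 0.75 × 120 = 90 mg to 0.75 × 360 = 270 mg.
- Methadone: 90 / 20 = 4.5 mg up to 270 / 3 = 90 mg, which the cap brings to 60 mg.

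Most values in between (9, 18, 22.5, 27, 36, 54, for example) are not multiples of 15, but a range this wide supports no count of patients.

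**Added opioid.** It is tempting to write 100% + 75% = 175% of baseline in the methadone arm. That needs an unchanged infusion, which no section states, and a cap that does not bind. In the capped case above, the added share falls to 75% × 60 / 90 = 50%. The opposite scenario, methadone at 75% against nothing in control, contradicts STUDY DESIGN & OBJECTIVE, which gives control patients continuous sedation. Neither figure describes the trial as written.

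**Order of events.** Under SCREENING/ENROLLMENT the signed order with the blinded dose goes to the investigational pharmacy. Under RANDOMIZATION the pharmacist assigns the next arm on the strength of that information. The dose is therefore settled before the arm is known.

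**The case for a change.** The strongest contrary case is that these gaps concern the intervention itself, which no analysis plan can repair. The cross-tolerance deduction does read like replacement arithmetic, and the usual sedation does contain an opioid. Further, if the 5 mg step applies to the daily total, an order for 40 mg reaches a pharmacist who knows the allocation and must decide how to divide it. Dispensing labels that give a capsule count per dose also suggest equal doses.

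Part of this stands. The protocol is silent on the running opioid and on rounding, and a single sentence on each would help those who deliver the treatment. But silence is not contradiction: TREATMENT SCHEDULE says the dose is based on earlier opioid intake, not that it takes its place, and a reduced and capped add-on dose can be scaled that way. Whatever masked staff do with the infusion, they do without knowing the arm, so an average difference in background opioid between arms would be a consequence of the assigned treatment.

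The pharmacist's division of an order leaves the daily total unchanged unless the pharmacist also rounds it. In the placebo arm the number of lactose capsules delivers no opioid in any case.

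**Conclusion.** No change to the plan is called for. Followed as written, the trial is a blinded, randomised comparison of methadone against placebo, each on top of continuous sedation, with one dose calculation for both arms. The capsule supply produces a modest departure from the calculated dose: at most 7.5 mg a day with equal doses rounded to the nearest capsule, more if rounding goes one way only, and none for multiples of 5 mg from 15 to 60 mg a day if unequal doses are used. That departure affects how precisely the dose is described, not the validity of the comparison.

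This rests on the dose being ordered before allocation, as the protocol sets out, and on the assignment of continuous sedation to both arms being honoured. The handling of the running opioid and the rounding convention are details the sponsor may wish to write down, in the same words for both arms, so that the objective, the dose rule and the dispensing instructions read as one. Their content is a clinical choice, and no better statistical method is being passed over by leaving it there.
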